6.2 Visits to a specialist clinic under the study

6.2.1 Screening visit (day 0, visit 1)

All patients will use ZOLEDRONIC ACID ACTAVIS in accordance with the decision of the treating physician and in accordance with the conditions contained in the Summary of Product Characteristics. In the Observation Form the following information will be recorded:

- » patient number
- » patient initials
- demographic data
- » data on primary disease
- » data on treatment with ZOLEDRONIC ACID ACTAVIS
- » concomitant diseases on the basis of medical history
- » data on pharmacotherapy of concomitant diseases
- » determination of the inclusion and exclusion criteria
- » data on tolerance of treatment with ZOLEDRONIC ACID ACTAVIS in opinion of the patient
- » data on adverse events related to treatment with **ZOLEDRONIC ACID ACTAVIS**.

6.2.2 Control visit 2 at least two months from the date of 1st visit according to the date of the planned visit arising from clinical needs of the patient

Patients will be reported on visits to the center for a set period of time. These visits will be conducted in accordance with the plan as part of routine follow-up of the Patient and time set according to the individual clinical needs. During these visits, the Investigators will collect and recorded in the Observation Form (CRF) information on the current course of the primary disease, its current treatment, adverse events related to treatment with ZOLEDRONIC ACID ACTAVIS, potential changes of pharmacotherapy used in primary disease and concomitant disease treatment and assessment of tolerance treatment with ZOLEDRONIC ACID ACTAVIS in the opinion of the patient.

7. ASSESMENT PERFORMED IN THE STUDY

The study project is not an evaluation of the effectiveness of treatment with **ZOLEDRONIC ACID ACTAVIS**.

7.1 Safety endpoints and methods of its evaluation

7.1.2. Related adverse events

Data on adverse events related to treatment with **ZOLEDRONIC ACID ACTAVIS** will be collected during the observation period and will also include adverse events occurring before enrolment to the Study. Information on these events will be collected during visits to specialist clinics based on directly asked questions in the survey. Doctors are required to report observed related adverse events to [contact]. For further description on reporting of adverse events please see Section 9.

7.2 Tolerance endpoints and methods of its evaluation

Data on adverse events and tolerability of treatment with **ZOLEDRONIC ACID ACTAVIS** in Patient opinion will be collected during the observation period as a response to the survey questions regarding these aspects during 1 single visit or 2 consecutive visits to specialist clinics.

8. STUDY DRUG

8.1 Administration of the drug

The drugs will be used based on a recommendation by the treating doctor, after realizing the prescription at the public pharmacy.

Study drug

ZOLEDRONIC ACID ACTAVIS is a formulation containing the active substance having the chemical name zoledronic acid (as monohydrate)

Pharmaceutical form: sterile, clear and colourless concentrate for infusion.

Potency: one ml concentrate contains 0.8 mg zoledronic acid (as monohydrate)

List of experiences: mannitol, sodium citrate, water for injections

Name and address of the manufacturer responsible for batch release:

Actavis Group PTC ehf. [name]

Description: sterile, clear and colourless concentrate for infusion.

8.2. Drug delivery

Not applicable

8.3. Patients identification

During the conduct of the study, all patients participating in it must be identifiable. The Investigator will conduct the list of Patients numbers and their names, so that their identification will be possible according to this list in the future, if necessary. The list of patients enrolled in the study should be stored confidentially at the study center.

Patient number will be assigned at baseline according to the chronological order of inclusion in the study in the center. Patients in the course of this study will be identified by a unique identification number consisting of a number of the center and the number of the patient. Patient and center numbers will be recorded in the Observation Form.

8.3 Concomitant medication

Data on other drugs used concomitantly with **ZOLEDRONIC ACID ACTAVIS** will be recorded in the Observation Form on every visit.

9. REPORTING RELATED ADVERSE EVENT

9.1 The division of adverse events

The related adverse events occurring during the treatment with the study drug is each related adverse events that follows during the active phase of the study, if:

» it was not present prior to the first dose of study drug

or

» it was presented before the first dose of study drug administration but its intensity was increased during the non-interventional Study

or

» it was presented before the first dose of study drug administration, its intensity did not changed but during the non-interventional Study found an association between administration of the study drug and the onset of this effect.

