9.2. Recording and monitoring the further course-related of adverse events

During each visit patients well-being will be recorded.

Each related adverse events will be recorded on the relevant pages of the Observation Form. The related adverse event should be recorded, including drug reactions, disease beginning during the observation or exacerbation of pre-existing disease.

Previously reported related adverse event which is recognized as "ongoing" shall be checked during each subsequent assessment.

For each recorded related adverse events Investigator must seek to obtain adequate information to determine the course of the related adverse events and to assess whether it meets the criteria for the classification of a related serious adverse event, that requires immediate (within 24 hours) notification to the Study Organizer. The Investigator must assess the causal relationship between the study drug administration and the occurrence of related adverse events and record the results of the evaluation in the Observation Form. Discontinuation of treatment with the study drug is necessary if the related event or its consequences are still present the next day after the related adverse event was recorded. Further monitoring is needed to down grade the event or its consequences, or to stabilize them at a level acceptable by investigator or a designated representative from the Office Study Organizer.

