10.4.3. The safety assessment

All safety data will be included in the summaries of data on individual patients. Analysis and summary tables are based on data from the safety population

The related adverse events will be coded in accordance with Medical Dictionary for Regulatory Activities (Med-DRA).

The prevalence of all reported related adverse events and serious adverse events occurring during the study drug administration will be presented in the form of tables. In addition, summary tables will be presented, that will include data on the maximum severity, relationship to the study drug administration and related data on adverse events, and patients who discontinued treatment with study drug for any reason.

The related adverse events occurring during the study will be noted in the tables related to adverse events. Medication usage due to concomitant disease will be summarized with the number and percentage of patients receiving them divided into a group of pharmacological and generic name of the drug.

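### The protocol gives competing windows for which related adverse events count, and one limb of its rule admits unchanged conditions that predate the first dose

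*Protocol*

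**What the plan says.** Protocol Section 3.2 names one endpoint, related adverse events, and Sections 10.4 and 10.4.3 report their frequency in the safety population. Four sections bear on which events enter that count.

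- Section 7.1.2: data on related events "will be collected during the observation period and will also include adverse events occurring before enrolment to the Study".
- Section 9.1: the definition opens with events during treatment, then narrows to "each related adverse events that follows during the active phase of the study". The active phase is not defined. Three alternative conditions follow, each anchored to the first dose. The first is that "it was not present prior to the first dose of study drug". The second covers conditions present before the first dose that worsened. The third covers conditions present before the first dose where "its intensity did not changed but during the non-interventional Study found an association between administration of the study drug and the onset".
- Section 9.2: the events to record include "disease beginning during the observation or exacerbation of pre-existing disease".
- Section 10.4.3 uses two windows. One sentence reads "The prevalence of all reported related adverse events and serious adverse events occurring during the study drug administration will be presented"; a later one reads "The related adverse events occurring during the study will be noted in the tables related to adverse events".

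Sections 5.2 and 5.3 require at least 30 days of treatment before enrolment and set no maximum. Section 3.3.1 plans about four months of observation. Section 6.2.2 places Visit 2 at least two months after Visit 1. Table 1 makes Visit 2 conditional on routine care, and Section 7.2 accepts a single visit.

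**The concern.** Treatment always starts before enrolment, so time since first dose and time since Visit 1 are different periods for every patient. A rule that moves between them does not identify one set of events. The choice matters most for reactions to the first infusion, which come before Visit 1 in every patient if they are prompt. It also matters for single-visit patients, whose recorded exposure lies wholly before enrolment.

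If recalled and observed events are pooled, the percentage depends on how long each patient had already been treated. It then cannot be read as a risk over any stated period.

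The third limb raises a separate problem. Read literally, it counts a condition whose onset came before any exposure to the drug. Some listed reactions in Section 1.2, such as bone pain and anaemia, can also be features of the disease or its treatment, so the wording is not harmless.

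**Working it through.** The plan has no figure to reproduce. Section 10.3 says that the 3,500 patients reflect practical limits, and the protocol gives no expected event rate. The check is therefore a comparison of the rules, followed by an illustration.

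**Step 1. Apply each rule to four cases**, reading the active phase and the study as starting at Visit 1.

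| Case | 7.1.2 | 9.1 | 10.4.3, on-drug sentence | 10.4.3, in-study sentence |
|---|---|---|---|---|
| Began after first dose, resolved before Visit 1 | counts | does not count | counts | does not count |
| Began after first dose, ongoing at Visit 1 | counts | unclear | counts | unclear |
| Began after Visit 1 | counts | counts | counts | counts |
| Present and unchanged since before first dose | only if called related | counts under limb three if an association is found | only if called related | only if called related |

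Only the third case is treated alike throughout without further conditions.

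**Step 2. Set the third limb beside its neighbours.** Section 9.2 names new disease and worsening, not unchanged disease, although its list is introduced as non-exhaustive. Section 9.1.3 collects only events with a causal relationship and ties possible and probable relationships to a likely time sequence. An onset before the first dose fails that criterion, yet limb three admits it.

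**Step 3. Illustrate the size of the window problem.** Inputs: N = 3,500 (Section 10.3); prior treatment P of at least 30 days (5.2); follow-up F of 0, 60 or 120 days (7.2, 6.2.2, 3.3.1). Assumptions not in the documents: a constant hazard of 1% per 30 days, the same P and F for all patients, and the chosen values of P above 30 days.

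- Counted in-study: 1 − exp(−0.01 × F/30)
- Counted since first dose: 1 − exp(−0.01 × (P + F)/30)
- Share of on-drug time before enrolment: P/(P + F)

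| P (days) | F (days) | In-study | Since first dose | Share before enrolment |
|---|---|---|---|---|
| 30 | 0 | 0 (0%) | 35 (1.0%) | 100% |
| 30 | 60 | 69 (2.0%) | 103 (3.0%) | 33% |
| 30 | 120 | 137 (3.9%) | 171 (4.9%) | 20% |
| 90 | 120 | 137 (3.9%) | 237 (6.8%) | 43% |
| 365 | 120 | 137 (3.9%) | 522 (14.9%) | 75% |

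For the third row: 1 − exp(−0.04) = 0.0392, times 3,500 = 137; and 1 − exp(−0.05) = 0.0488, times 3,500 = 171.

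No such calculation is possible for limb three. The protocol does not give the share of patients with an unchanged pre-dose condition, or the share of those that an investigator would attribute to the drug.

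**The case against.** The strongest reply is that most of the text points to one window. Section 9.1 opens with events during treatment and anchors to the first dose, 7.1.2 includes pre-enrolment events, and the main table in 10.4.3 covers time on drug. On this view the active phase and the in-study sentence are stray wording. That is a fair account of the balance, and it supports choosing first infusion as the window. It does not remove the conflict, because investigators and analysts must still choose between the statements.

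A second reply is that the first dose means the first dose within the study. Limb three would then cover ongoing pre-enrolment reactions recognised later. The protocol does not say this, and reactions that resolved before Visit 1 would still be in under 7.1.2 and out under 9.1.

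A third is that the causality filter in 9.1.3 keeps out limb-three cases. It may keep out most or all of them. A reader might infer that limb three contaminates the results; the documents support only that it could. Nor is the 70–95% pain figure in Section 1.1 the pool exposed to limb three. The same paragraph also gives 49%, and neither figure is limited to pain that was present before the first dose, unchanged and attributed to the drug.

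A fourth is that table layout belongs in a statistical analysis plan, which is not shown, and that the study is descriptive and disclaims definitive conclusions (10.3). Layout can indeed be settled there. The contradiction, however, is in protocol text that governs what is collected, and a descriptive percentage still needs one numerator and a time base.

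**Conclusion.** The point holds for the adverse event frequencies. At least two windows, since first dose and since Visit 1, can be read from the protocol, and they give different percentages. In the illustration the difference is 3.9% against 4.9% at the minimum prior treatment and 120 days of follow-up, and it grows with longer prior treatment. Those figures rest on an assumed hazard and uniform exposure times, and show scale only. Limb three conflicts with 9.1.3 and is not supported by 9.2; its effect is unknown and may be small.

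A reader might infer more than this. The demographic, disposition and concomitant medication tables do not use the rule and are unaffected. A ceiling on prior treatment might be inferred from the January 2013 registration and the January 2015 date of the product information, but neither is an enrolment date or a Polish launch date, so no upper bound can be stated. Nor do the documents give a reason to make post-Visit-1 events the primary table. That would demote reactions to the first infusion and leave single-visit patients contributing nothing.

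**What to change.** 1. State one window, from the first infusion of the study drug, in the same words in Sections 7.1.2, 9.1, 9.2 and 10.4.3.
2. Define the active phase and the first dose.
3. Delete the third limb of 9.1, or reword it so that onset must follow the first dose.
4. Make sure that the Observation Form captures the date of first infusion and the onset date of each event. The form is not shown. Section 6.2.1 lists treatment data and 9.1.3 asks for time-sequence information, so the dates may already be there.
5. Tabulate events from first infusion to Visit 1, labelled retrospective, separately from events after Visit 1. Give each table its own denominator and exposure time; neither needs to be primary. This step can be placed in the statistical analysis plan.

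The cost is wording in four sections, at most two dates on the form, and one extra table set. The dates should be secured before forms are completed: without them the two periods cannot be reliably separated at analysis.

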9.1.1. The term Serious Adverse Event

Serious adverse events are adverse events occurring regardless of the dose, that:

- 1. Causes death.
- 2. Constitutes a threat to life, which means that the action is related to a direct threat to life of the patient. It does not include a reaction that, if it had occurred in a more serious form, could have resulted in death.
- 3. This leads to hospitalization or prolongation of a previous patient's hospitalization, with the exception of the admission of the Patient to the hospital for social or administrative reasons.
- 4. It causes permanent or significant health detriment.
- 5. This leads to congenital malformations or perinatal damage.
- Other effects of the medicinal product, that physicians according to his knowledge, considers medically important.

Regardless of the above criteria each adverse events that investigator considers as serious, should immediately (within 24 hours) be reported by e-mail to Office of Study Organizer: [contact] or by [contact], see section 9.6. Office of Study Organizer will be trained in how to report ADRs from this study to Sponsors PV Drug Safety via the Person Locally Responsible for Pharmacovigilance (PLRP) in Actavis Poland, [name], [name]; [name]; e-mail: [name]. This training will be documented. The flow of the SAEs are visualized in a flow chart in the Safety Management plan.

Hospitalization is defined as each admission of the patient to the hospital (also a period of less than 24 hours). In the case of protracted or long-term hospitalization, the hospitalization is considered to be a transfer within the patient's hospital in intensive care.

Prolonged hospitalization is definied as each prolongation of hospitalization outside the required time for the initial reason for admission of the patient to the hospital in the opinion of the Investigator or Doctor from the hospital.

9.1.2 Classification by severity

The related adverse events will be classified as mild, moderate or severe according to the following criteria:

- Mild: symptoms do not alter the normal functioning of the Patient
- Moderate: symptoms cause some degree of dysfunction of the Patient, but are not dangerous, unpleasant or embarrassing to the Patient.
- Severe: symptoms are clearly dangerous for the Patient, cause significant impairment functioning or disability.

9.1.3. Classification according to the a causal relationship between the use of the administered drug and the occurrence of an adverse event

In the Study only adverse events data showing a causal-and-effect relationship with the administration of the study medicinal product will be collected.

Submission of possible and probable (likely time sequence, dose-response relationship) and certain adverse events (good response to discontinuation of the drug or the severity of the adverse events after restarting the drug) related to study medicinal product use will be reported. This report should also include the correct reason and comprehensive information covering the likely time sequence, a good response to treatment withdrawal/reduction of the dose or the severity of the adverse event after restarting the drug/increase the dose; another used pharmacotherapy and procedures – dose decrease, drug withdrawal, optional treatment administered, the effect of used procedure.

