When initiating treatment with Zoledronic acid Actavis in patients with multiple myeloma or metastatic bone lesion from solid tumors, serum creatinine and creatinine clearance (CLcr) should be determined. CLcr is calculated from serum creatinine using Cockcroft-Gault formula. Zoledronic acid Actavis is not recommended from patients presenting with severe renal impairment prior to initiation of therapy, which is defined for this population as CLcr < 30 ml/min.

In patients with bone metastases presenting with mild to moderate renal impairment prior to initiation of therapy, which is defined for this population as CLcr 30-60 ml/min, the following Zoledronic acid Actavis dose is recommended:

- » baseline creatinine clearance > 60 ml/min Zoledronic acid Actavis recommended dose is 4.0 mg zoledronic acid,
- » baseline creatinine clearance 50-60 ml/min Zoledronic acid Actavis recommended dose is 3.5 mg zoledronic acid,
- » baseline creatinine clearance 40-49 ml/min Zoledronic acid Actavis recommended dose is 3.3 mg zoledronic acid,
- baseline creatinine clearance 30-39 ml/min Zoledronic acid Actavis recommended dose is 3.0 mg zoledronic acid.

Following initiation of therapy, serum creatinine should be measured prior to each dose of Zoledronic acid Actavis and treatment should be withheld if renal function has deteriorated. In the clinical trials, renal deterioration was defined as follows:

- » For patients with normal baseline serum creatinine (<1.4 mg/dl or <124 micromol/l), an increase of 0.5 mg/dl or 44 micromol/l;
- » For patients with abnormal baseline creatinine (>1.4 mg/dl or >124 micromol/l), an increase of 1.0 mg/dl or 88 micromol/l.

In the clinical studies, zoledronic acid treatment was resumed only when the creatinine level returned to within 10% of the baseline value. Zoledronic acid Actavis treatment should be resumed at the same dose as that given prior to treatment interruption.

Patients must be assessed prior to administration of Zoledronic acid Actavis to ensure that they are adequately hydrated. Overhydration should be avoided in patients at risk of cardiac failure.

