Standard hypercalcaemia-related metabolic parameters, such as serum levels of calcium, phosphate and magnesium, should be carefully monitored after initiating Zoledronic acid Actavis therapy. If hypocalcaemia, hypophosphataemia, or hypomagnesaemia occurs, short-term supplemental therapy may be necessary. Untreated hypercalcaemia patients generally have some degree of renal function impairment, therefore careful renal function monitoring should be considered. Case of severe hypocalcaemia requiring hospitalization have been reported. In some instances, life-threatening hypocalcaemia may be encountered.

Other products containing zoledronic acid as active substance are available for osteoporosis indications and treatment of Paget's disease of the bone. Patients being treated with Zoledronic acid Actavis should not be treated with such products or any other bisphosphonate concomitantly, since the combined effects of these agents are unknown.

The recommended dose in hypercalcaemia induced by malignance proces (albumin – corrected serum calcium ≥12.0 mh/dl or 3.0 mmol/l) is a single dose of 4 mg zoledronic acid.

Zoledronic acid Actavis treatment in TIH patients who also have severe renal impairment should be considered only after evaluating the risk and benefits of treatment. In the clinical studies, patients with serum creatinine >400 micromol/l or >4.5 mg/dl were excluded. No dose adjustment is necessary in TIH patients with serum creatinine < 400 micromol/l or <4.5 mg/dl.

Interaction of ZOLEDRONIC ACID ACTAVIS formulation with other medication products

In clinical studies, zoledronic acid has been administered concomitantly with commonly used anticancer agents, diuretics, antibiotics and analgesics without clinically apparent interactions occurring.

Zoledronic acid shows no appreciable binding to plasma proteins and does not inhibit human P450 enzymes in vitro, but no formal clinical interaction studies have been performed.

Caution is advised when bisphosphonates are administered with aminoglycosides, calcitonin or loop diuretics, since agents may have an additive effects, resulting in the lower serum calcium level longer periods than required.

Caution is indicated when Zoledronic acid Actavis is used with other potentially nephrotoxic medical products. Attention should also be paid to the possibility of hypomagnesaemia developing during treatment.

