9.1.5. Deviations in the results of laboratory tests

Liver enzymes, total blood count, serum creatinine, uric acid and electrolytes concentrations, if these tests were made.

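### The severity scale in section 9.1.2 has no criterion for reactions defined by a laboratory value, so the maximum-severity summary cannot reflect how large asymptomatic laboratory changes were

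*Protocol*

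**What the plan says.** Protocol section 9.1.2 sets one scale for all related events: "The related adverse events will be classified as mild, moderate or severe according to the following criteria". The lowest of the three grades is "Mild: symptoms do not alter the normal functioning of the Patient". The middle grade again starts from symptoms and limits what they may involve: "Moderate: symptoms cause some degree of dysfunction of the Patient, but are not dangerous, unpleasant or embarrassing to the Patient". The top grade keeps the same subject but brings in danger and disability: "Severe: symptoms are clearly dangerous for the Patient, cause significant impairment functioning or disability".

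Section 9.1.5, within the same adverse event section, puts laboratory deviations in scope: "Liver enzymes, total blood count, serum creatinine, uric acid and electrolytes concentrations, if these tests were made". It gives no threshold or grade, and it does not say whether the value, unit or reference range is recorded. No laboratory grading scale is named anywhere in the protocol.

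Section 10.4.3 uses the grade in the output: "summary tables will be presented, that will include data on the maximum severity".

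The product information in section 1.2 lists hypophosphataemia as the only very common reaction (1 in 10 or more). Hypocalcaemia and increased blood creatinine and urea are common (1 in 100 to below 1 in 10). Hypomagnesaemia, hypokalaemia, thrombocytopenia and leukopenia are uncommon.

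**The concern.** The scale asks what the patient feels and how the patient functions. Several of the reactions listed for this drug, including the most frequent one, are laboratory values that can be abnormal without symptoms. For those the scale has nothing to measure: a slight and a pronounced asymptomatic change look the same on it.

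Safety is the main aim of the study, and maximum severity is one of the few planned safety outputs. If the grade of a laboratory reaction depends on each investigator's improvisation, the severity summary says little about that class of reaction, and a reader may take a run of mild entries as reassurance about magnitude.

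**Working it through.** The plan states no figure on this point to reproduce. The check is mainly a reading of the sections against each other.

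**Step 1. Scope of the scale.** Section 9.1.2 covers all related adverse events and makes no separate provision for laboratory events. Section 9.1.5 places creatinine, electrolytes, blood count, liver enzymes and uric acid within section 9.1. The scale is therefore the only one available for them.

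**Step 2. Apply each grade to a laboratory reaction without symptoms.**

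| Grade | What the definition requires | Asymptomatic laboratory change |
|---|---|---|
| Mild | symptoms present, functioning normal | functioning is normal, but there are no symptoms |
| Moderate | symptoms causing some dysfunction | not met |
| Severe | symptoms that are dangerous or seriously impairing | no symptoms, although an investigator might lean on the reference to danger |

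Read literally, no grade applies. Mild is the most natural default because functioning is unaltered. Leaving the event ungraded, or calling it severe because it is dangerous, is also open to an investigator.

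**Step 3. Is this class of event real in this protocol?** Section 1.2 says that "treatment should be withheld if renal function has deteriorated" and reports that earlier trials defined deterioration as a creatinine rise of 0.5 mg/dl from a normal baseline or 1.0 mg/dl from an abnormal one. That is background text and not a severity grade. It shows only that renal deterioration is recognised there by a measured value, with no symptom required. Section 1.2 also expects creatinine before each dose and monitoring of calcium, phosphate and magnesium, and section 3.1 says treatment should follow the product label. Results of this kind should often exist in routine care, though how completely is unknown.

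**Step 4. Scale, as illustration only.** Inputs from the protocol: about 3,500 patients (section 10.3) and the frequency bands in section 1.2.

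- Hypophosphataemia at the band's lower limit, all patients tested: 3,500 × 0.10 = 350.
- Each common laboratory reaction, all patients tested: 3,500 × 0.01 = 35 to below 3,500 × 0.10 = 350.

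Assumptions that are not in the documents: 25% to 100% of patients tested, 5% to 30% of cases above mild on a laboratory-value scale, and all cases asymptomatic. The number of hypophosphataemia cases that a numeric scale would place above mild is 350 × share tested × share above mild:

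- low end: 350 × 0.25 × 0.05 = 4.4
- high end: 350 × 1.00 × 0.30 = 105

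Nothing in the protocol narrows this range. The 350 is not a floor for this study either, because tests are recorded only if made and only events judged related to the drug are collected (section 9.1.3).

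**The case against.** **Important cases are caught elsewhere.** Seriousness is judged separately in section 9.1.1, with a criterion for medically important effects. Section 10.4.3 also tabulates related events, serious events and discontinuations. This stands, and it confines the problem to the severity summary: frequencies and serious-event reporting do not depend on the grade. It does not repair that summary, and a substantial but non-serious change stays invisible there.

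**Laboratory grading is a matter for the SAP.** The layout of the tables is. But the investigator assigns the grade at source, under criteria the protocol fixes. If the value, unit and reference range were not captured, no later plan could regrade the event.

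**Stronger readings that the documents do not support.**

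- A reader might infer that every asymptomatic laboratory reaction must be graded mild whatever its depth. No section says so; the literal position is that no grade applies.
- A reader might infer that the whole safety profile is biased in the drug's favour. Only the severity summary is touched, and section 10.3 itself disclaims definitive safety conclusions.
- A reader might point to the severe hypocalcaemia described in section 1.2. Those cases involve hospitalisation or threat to life, which meet the seriousness criteria and fit the reference to danger in the severe grade. They are the cases that the present rules handle best.
- A reader might see a contradiction between the creatinine definition in section 1.2 and the grades in 9.1.2. A threshold quoted as dosing background is not a severity grade, and the protocol does not equate the two.
- A reader might argue that event counts are affected too, since section 9.1 counts a pre-existing event if its intensity increased. Section 9.1 does not tie intensity to the grades in 9.1.2, so this cannot be established.

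**Conclusion.** The point holds as a gap in a rule that the protocol does state. Section 9.1.2 applies a symptom-only scale to all related events, section 9.1.5 includes laboratory deviations, and section 10.4.3 reports maximum severity. For laboratory reactions without symptoms the grade is undefined. It will probably default to mild or vary between investigators, and the summary cannot reflect the magnitude of these reactions.

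Understatement is the likelier direction but not certain. Its size cannot be determined from the documents; the range of about 4 to 105 hypophosphataemia cases rests entirely on assumed testing rates and severity distributions. Laboratory reactions that do cause symptoms can still be graded on the existing scale. This is a worthwhile and inexpensive correction, not a flaw that undermines the study.

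**What to change.** In section 9.1.2:

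1. Keep the symptom scale for clinical events.
2. For reactions defined by a laboratory value, name one fixed numeric laboratory grading scale and state how its grades map to mild, moderate and severe. The sponsor should confirm that the chosen scale has cut-offs for the laboratory reactions listed in section 1.2, which cannot be checked here.
3. Where the test was made in routine care, record the value, unit and reference range on the observation form.

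In section 10.4.3, show maximum severity separately for laboratory and clinical events, with laboratory events that lack a recorded value shown as not gradable.

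No additional test or procedure is needed, so the study remains non-interventional. The cost is one paragraph, a few form fields and one derived variable. Some events will be ungradable because routine results are incomplete, a numeric grade will replace the investigator's judgement for laboratory events, and more events will probably appear as moderate or severe.
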